### ***Analysis of all TEAEs***

The following TEAE summaries will be generated for the safety population.

- Overview of TEAEs, summarizing number (%) of patients with any
  - TEAE
  - Serious TEAE
  - TEAE leading to permanent treatment discontinuation
  - TEAE leading to death
  - Serious TEAE leading to permanent treatment discontinuation
- All TEAEs by primary SOC and PT, sorted by the internationally agreed SOC order and by decreasing incidence of PTs within each SOC. This sorting order will be applied to all other tables by SOC and PT, unless otherwise specified.
- All TEAEs related to IMP by primary SOC, and PT
- All TEAEs by maximal severity, presented by primary SOC and PT
- Common TEAEs (e.g., PTs  $\geq 2\%$  in any treatment group) by primary SOC, and PT
- Common TEAEs (e.g., PTs  $\geq 5\%$  in any treatment group) by primary SOC and PT and by intrinsic factors: age group ( $<50$ ,  $\geq 50$  to  $<65$ ,  $\geq 65$  to  $<75$ ,  $\geq 75$  years), sex (Male, Female), race (White, Black or African American, Asian, Other), and any pertinent subgroups as appropriate.
- All TEAEs by primary SOC and PT and by subgroup BMI ( $<30$ ,  $\geq 30$  to  $<40$ ,  $\geq 40$  kg/m^2)
- All TEAE by primary SOC and PT and by anti-efpeglenatide antibody status (positive, negative)
- Kaplan-Meier plot, for the time to first onset of the following PTs: nausea, vomiting and diarrhea

- The frequency of TEAEs over time will be provided for nausea, vomiting and diarrhea, using 3-month time intervals, i.e., [0-3] month, (3-6] month, (6-9] month, (9-12] month, etc. In each time interval, the numerator in the calculation of percentages will be the number of participants with at least 1 TEAE occurring in this time interval. Two types of analyses will be included:
  - (1) only the first event will be counted for each participant and all recurrent events will not be included, and the denominator for the calculation of percentages will be the number of participants at risk at the beginning of the time interval who did not experience a first event in the preceding intervals;
  - (2) the recurrent events in subsequent intervals will be counted once for each participant in the numerator of the corresponding interval, and the denominator for the calculation of percentages will be the number of participants at risk at the beginning of the time interval.

A histogram of the frequency over time (by 3-month intervals) will also be presented as appropriate.

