Clinical chemistry ^g	X		X	X	X		X		X	X	X	X	X	
Lipid profile ^h	X			X			X			X		X		
Amylase, lipase, and calcitonin	X		X	X	X		X		X	X	X	X	X	
Urinalysis	X													Urine analysis: pH, glucose, ketones, leucocytes, blood/hemoglobin, protein.
Urinalysis (spot)	X		X	X	X		X		X	X		X		Urinary albumin-to-creatinine ratio (UACR) performed by spot urine
Pregnancy test (WOCBP only) ⁱ	X		X	X	X		X		X	X		X	X	

	Screening		Intervention Period ^b							Participants who prematurely discontinued IMP		Participants who did not prematurely discontinue IMP		Notes
Month			0	3	6	9	12/ 24/ ...	15/21/ 27/ ...	18/30/ ...					
Week	-3	-1	0	12	24	36	48/96/ ...	60/84/ 108/...	72/120/ ...					
Visit	1	2	3 R	4	5	6 ☎	7/11/...	8/10/12/... ☎	9/13/...	pEOT ^c	Study closeout ^d	Study closeout ^d	Follow-up	
Acceptable range (days)	+7 ^a	± 3 ^a		± 7	± 7	± 7	± 7	± 7	± 7				Closeout + 6 weeks	
Anti-efpeglenatide antibody sampling			X	X	X		X			X		X ^j		Samples will be drawn before the IMP dosing at the site

- a There must be not more than 3 weeks + 3 days between screening visit and randomization. In some cases, Visit 2 might be combined with Visit 3 (Randomization), as per Investigator's judgement, according to the patient's medical profile.
- b Additionally, in between each on site visit, starting after Visit 5, participants will be contacted by phone to collect endpoint events, IMP administration information, and safety data.
- c If a participant prematurely permanently discontinues treatment with IMP, the participant will undergo a pEOT Visit as soon as possible. Participants will then continue in the study with all study procedures/visits except those associated with IMP administration. Participants will continue to be followed after a CV or renal endpoint occurs irrespective of their treatment status. If the participant does not agree to site visits, he/she will be contacted by telephone to inquire about safety status (including hospitalizations and endpoints).
- d All randomized participants will be asked to return to the study site for a Study Closeout Visit when primary 3-point MACE are positively adjudicated in approximately 330 participants. The timing and window of this visit will be communicated to sites. For participants who previously prematurely permanently discontinued IMP, there must be at least 6 weeks between the last IMP administration and the Study Closeout Visit, the Study Closeout Visit will be the final study visit, and no further visits are planned.

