#### ***Observation period***

The observation period will be divided into 3 periods:

- The pre-treatment period or screening period is defined as the time from signed informed consent up to the time of first injection of the double-blind IMP
- The treatment-emergent adverse event period (on-treatment period) is defined as the time from the first injection of the IMP to the last injection of the IMP + 30 days (or +7 days for hypoglycemia).
- The posttreatment period is defined as the period after the end of the treatment-emergent adverse event period.

The on-study observation period/on-study is defined as the time from first IMP until the end of (the) study date (defined as the last scheduled visit for those who completed the study and the study discontinuation date collected on eCRF form 'Completion of End of Study' for those who did not complete the study. If death is reason collected on the 'Completion of End of Study' form, date of death will be used).

The post-study observation is defined as anything after the on-study observation period.

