#### ***2.3.5.1 Analyses of adverse events***

##### ***Generalities***

The primary focus of AE reporting will be on TEAEs. Pretreatment and posttreatment adverse events will be described separately.

If an adverse event date/time of onset (occurrence, worsening, or becoming serious) is incomplete, an imputation algorithm will be used to classify the adverse event as pretreatment, treatment-emergent, or posttreatment. The algorithm for imputing date/time of onset will be conservative and will classify an adverse event as treatment emergent unless there is definitive information to

determine it is pretreatment or posttreatment. Details on classification of adverse events with missing or partial onset dates are provided in [Section 2.5.3](#).

Adverse event incidence tables will present by SOC and PT, sorted in alphabetical order for each treatment group, the number (n) and percentage (%) of patients experiencing an adverse event. Multiple occurrences of the same event in the same patient will be counted only once in the tables within a treatment phase. The denominator for computation of percentages is the safety population within each treatment group.

Sorting within tables ensures the same presentation for the set of all adverse events within the observation period (pretreatment, treatment-emergent, and posttreatment). For that purpose, the table of all TEAEs presented by SOC and PT sorted by the internationally agreed SOC order and decreasing frequency of PTs within SOCs will define the presentation order for all other tables unless otherwise specified. Sorting will be based on incidence in the pooled efpeglenatide group.

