#### **2.4.5 Analyses of immunogenicity variables**

An anti-drug antibody positive participant is defined as a participant with at least one treatment-induced or treatment-boosted ADA-positive sample at any time.

Summaries of ADA data will be provided for participants treated with efpeglenatide only. All summaries related to kinetics of ADA response (ADA status and magnitude, ADA attributes, participant status, ADA incidence) will be descriptive; no statistical significance tests will be performed on ADA data. The incidence of ADA status (positive/negative/inconclusive) will be summarized by visit, treatment, and individual titer for the ADA population. Incidence of treatment induced and treatment-boosted (treatment emergent) ADA during on-study period will be summarized by treatment. Incidence of participants with ADA cross-reactivity to endogenous GLP-1 (positive/negative), and to endogenous glucagon (positive/negative) will be summarized by visit and treatment. Incidence of participants with ADA directed against PEG linker, HMC001 moiety and exendin-4 moiety (positive/negative), will be summarized by visit and treatment. Analysis will be conducted as appropriate to assess the relationship with hypersensitivity reactions.

Incidence of participants with neutralizing antibodies against efpeglenatide and against endogenous GLP-1 and Glucagon will be summarized by visit and treatment.

ADA data from unscheduled visits (due to SAE for example) will not be included in summary and will be presented only in ADA values listing.

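### The planned table of adverse events by antibody status ignores timing and exposure, so it can show a difference between ADA-positive and ADA-negative participants when there is none

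*SAP*

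**What the plan says.** SAP 2.3.5.1, under Analysis of all TEAEs, lists "All TEAE by primary SOC and PT and by anti-efpeglenatide antibody status (positive, negative" among the splits of the general TEAE table. That line does not define positive. The only definition is in SAP 2.4.5: "An anti-drug antibody positive participant is defined as a participant with at least one treatment-induced or treatment-boosted ADA-positive sample at any time".

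The form of the table comes from Generalities in SAP 2.3.5.1. AE tables give "the number (n) and percentage (%) of patients experiencing an adverse event", with the rule that "Multiple occurrences of the same event in the same patient will be counted only once in the tables within a treatment phase". On the denominator it says "The denominator for computation of percentages is the safety population within each treatment group". Under Observation period in SAP 2.1.4, an event is treatment-emergent during "the time from the first injection of the IMP to the last injection of the IMP + 30 days", so the window lengthens with time on drug.

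The sampling times are in Protocol 1.3, row "Anti-efpeglenatide antibody sampling": Weeks 0, 12, 24, 48, 96 and yearly after that, plus the premature end-of-treatment visit, or close-out for those still on drug. The row's note says "Samples will be drawn before the IMP dosing at the site".

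The one other planned link between antibodies and harm is a sentence in SAP 2.4.5 promising an analysis against hypersensitivity reactions, with no method given. The same section keeps antibody results from unscheduled visits out of the summaries and only lists them. Neither document requires event onset to follow the first positive sample, gives person-time by ADA status, or sets a landmark.

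**The concern.** ADA status is not a baseline factor like age, sex or BMI, the other splits in that list. It is settled by samples taken throughout follow-up, while the events it sorts may have happened much earlier. An event in Week 2 in someone first positive at Week 96 is shown as an event in an ADA-positive participant.

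Time on drug drives both sides of the comparison. More treatment means more samples that can turn positive and a longer window for events, so the groups differ in exposure before antibodies have any effect.

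Severe allergic reactions, severe injection-site reactions and severe immune complex disease are named in Protocol 8.3 for specific monitoring. Antibody data help to interpret such events, and this is the only fully specified table that puts the two together.

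**Working it through.** The plan states no figure for this table, so there is nothing to reproduce. The check has one part that needs only the documents and one that needs assumed rates.

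**1. Ordering, from the documents alone.** The first scheduled post-baseline sample is at Week 12. Titration runs to Week 8 (Protocol Table 1). Protocol 2.3 reports that nausea and vomiting rose after the first injection and then generally declined. Events in roughly the first 12 weeks therefore precede any post-baseline antibody result, unless an early end-of-treatment sample is taken. Nothing stops them being counted under ADA-positive later.

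**2. Opportunity, from the documents alone.** Someone treated for 36 months (about 156 weeks) has post-baseline draws at Weeks 12, 24, 48, 96 and 144 and at close-out: six. Someone who stops at Week 6 has one scheduled on-treatment draw, at the end-of-treatment visit.

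**3. Simulation with no true link.** Antibody conversion and event onset were generated independently, with 400,000 participants per scenario.
- From the documents: follow-up of 24 to 36 months, the sampling weeks above, and the window to last dose + 30 days.
- Assumed, set A: conversion 0.1 to 0.6 per year, event rate 0.05 to 0.3 per year, permanent stopping 5% to 20% per year.
- Assumed, set B: conversion 0.1 to 0.3 per year, event rate 0.02 to 0.1 per year, 20% to 30% stopping early at a mean of 0.6 years.
- In both sets sampling ends with treatment.

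Planned measure: R = (% of ADA-positive participants with an event) / (% of ADA-negative participants with an event). The right answer is 1 in every scenario.

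| Quantity, constant event hazard | Set A | Set B |
|---|---|---|
| Crude R | 1.04 to 1.45 | 1.17 to 1.43 |
| ADA-positive participants' first events before first positive sample | 49% to 65% | 55% to 61% |
| The same, before simulated conversion | 37% to 53% | 42% to 49% |

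In set A, mean time on drug was 2.2 to 2.5 years in ADA-positive and 1.5 to 2.3 years in ADA-negative participants. The middle case (conversion 0.3, events 0.3, stopping 10% per year) gave 51.8% v 45.6%, so R = 51.8/45.6 = 1.14.

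A hand check uses risk = 1 − exp(−rate × time), with that case's mean times of 2.39 and 2.04 years plus 30 days (0.08 years):
- positive: 1 − exp(−0.3 × 2.47) = 0.52
- negative: 1 − exp(−0.3 × 2.12) = 0.47
- ratio about 1.11

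Different time on drug thus accounts for most of the gap.

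**4. Does a time-updated rate repair it?** Status is negative until the first positive sample and positive afterwards. Rate = 100 × participants with a first event in that state / patient-years in that state. With a constant hazard the set A rate ratio was 0.98 to 1.03.

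With the event hazard 5 times higher in the first 12 weeks (an assumed multiple, in line with the GI pattern), it is not enough:

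| Measure, early-peaking events, no true link | Set A (stopping 10%) | Set B |
|---|---|---|
| Crude R | 1.06 to 1.15 | 1.11 to 1.27 |
| Time-updated rate ratio, no further adjustment | 0.52 to 0.60 | 0.60 to 0.68 |
| Time-updated, after Week 12 only | 1.00 | 0.98 to 1.02 |

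The unadjusted rate fails because the high-risk early weeks all fall in the negative state. Starting the clock at Week 12 removes this.

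**The case against.** **The table is descriptive.** Antibody endpoints are tertiary (Protocol Table 2), the SAP plans no tests on safety data, and SAP 2.4.5 rules them out for antibody data. This stands and limits the stakes. A two-column display still invites comparison.

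**Timing can be read case by case.** The Listing paragraph of SAP 2.3.5.1 requires listings of serious events and of events leading to discontinuation, with onset dates. SAP 2.4.5 lists antibody values, including unscheduled ones. Protocol 8.8.1 asks for samples 4 and 6 months after treatment from participants who are positive at study end and had a severe injection-site or hypersensitivity reaction. A reader might infer that the table would conceal a true link to reactions that end treatment. The listings mean the documents do not support that for serious or treatment-ending events. Severe reactions that are neither are not expressly covered.

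**Early stoppers may go on being sampled.** Protocol 7.1.1 keeps them on all procedures except those tied to drug administration, but the schedule marks no antibody draw at their close-out. Whether draws continue is unclear. Simulating continued sampling, with conversion only while on drug, still gave crude ratios of 1.17 to 1.42.

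**The rates are assumed.** This stands. At the low end, 1.04, the distortion is trivial.

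**Conclusion.** The point holds as a problem of interpretation in one exploratory safety display. The ordering part follows from the documents alone. The size does not: 1.04 to 1.45 under no true link, on assumed rates.

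Two stronger readings should be resisted. One is that the table must overstate events in ADA-positive participants. It did so in every null scenario run, but events that cause early stopping leave fewer samples and could move events into the ADA-negative column, so the net direction is unknown. The other is that more than half of the events counted as ADA-positive came before the antibodies. The 49% to 65% is measured against the first positive sample; against conversion itself it is 37% to 53%. For early-peaking events both shares rise, the first to 72% to 78%.

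The primary and secondary efficacy analyses are not touched.

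**What to change.** In SAP 2.3.5.1 and 2.4.5:

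- Keep the ever-positive table, labelled as not accounting for event timing or exposure. Use the ADA subgroup as denominator, since the general rule names the treatment group. Say where placebo participants and those without a valid post-baseline sample go.
- Add a display for efpeglenatide-treated participants in the ADA population, at least for hypersensitivity, injection-site and immune complex events. Status is negative until the first treatment-induced or boosted positive sample and positive afterwards. Report first events per 100 patient-years in each state, restricted to time after the Week 12 sample or split by time since first dose. Without that restriction the rate should not be used for early-peaking events.
- For reaction-type events, list the nearest antibody results before and after onset, including unscheduled samples.
- State whether antibody draws continue after the premature end-of-treatment visit.

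The SAP already uses rates per 100 patient-years (severe hypoglycemia) and interval-specific at-risk denominators (nausea, vomiting, diarrhea), so neither tool is new to it.

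The cost is wording, one derivation from dates already collected, and one listing. There are two limits. Conversion is dated late by up to one sampling interval, which is 48 weeks once sampling is yearly (Week 48 to Week 96). Events before Week 12 carry no information on this question beyond the listing.

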### 1.3 DETERMINATION OF SAMPLE SIZE

It is estimated that approximately 4000 participants are needed to obtain approximately 330 participants with a positively adjudicated event for the primary composite cardiovascular endpoint (3-point MACE), based on the following trial design characteristics assumptions:

[figure not shown]
- A recruitment period of approximately 12 months
- Study duration is estimated to be approximately 24 months of follow-up after the last randomized patient, estimated follow-up ranging from 24 to 36 months
- 2% annual early study discontinuation
- Yearly event rate in placebo group: 4.4% for participants not using a SGLT2 inhibitor, and 3.7% for participants using a SGLT2 inhibitor
- Treatment effect of efpeglenatide compared to placebo: 15% risk reduction for participants not using a SGLT2 inhibitor, and a neutral effect for participants using a SGLT2 inhibitor
- 20% of participants using a SGLT2 inhibitor at baseline, and additional 10% participants in placebo group and 5% participants in efpeglenatide group adding a SGLT2 inhibitor during the study period

This will provide:

- 90% power to demonstrate non-inferiority (NI) of efpeglenatide vs placebo with a 1.3 NI margin {upper bound of the 95% CI of the estimated hazard ratio <1.3} for the 3-point MACE (CV death, non-fatal MI or non-fatal stroke)
- >99% power to demonstrate NI with a 1.8 margin

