## 2 STATISTICAL AND ANALYTICAL PROCEDURES

### 2.1 ANALYSIS ENDPOINTS

#### **Key definitions:**

**Completion of Study:** as study approaches to the end, the team will make prediction of time window when the target 330 first occurrence of 3-point MACE (positively adjudicated) can be achieved. Once projected visit window is determined, the site will be notified of the time window. Following announcement of the project study close-out visit:

- 1) for subjects remaining on IMP at announcement of project study close-out visit, sites will schedule a study close-out visit and an off-drug follow-up visit as per the time and events scheduled in protocol;
- 2) for subjects that have prematurely and permanently discontinued IMP prior to announcement of the project study close-out visit but still in study at the announcement, sites will schedule a study close-out visit;
- 3) for subjects that have prematurely and permanently discontinued study prior to announcement, sites will be required to make a final contact for efficacy outcome collection (if patients allow further contact by family member and health provider) or vital status check (if allowed by local law) as soon as possible after the announcement.

**Scheduled study-close out visit:** a study visit window projected by the sponsor during which the sites are required to bring all patients back to site for study closeout. It is a fixed calendar time window. For patients who already discontinued study prematurely, they'll miss this visit and their efficacy events after this scheduled visit will not be included for efficacy analysis even positively adjudicate.

**Scheduled last study visit:** later of study closeout visit or follow-up visit. That is, for patients still on IMP at study close-out visit, their scheduled last study visit will be follow-up visit; while for patients not on IMP at study close-out visit, study close-out visit will be their scheduled last study visit.

**End of study date:** defined as date of last scheduled visit for those completed the study (follow-up visit or study closeout visit if premature discontinued IMP) and the date collected on eCRF form 'Completion of End of Study' for those who did not complete study. If death is reason collected on the 'Completion of End of Study', date of death will be used

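### The 3-month nausea, vomiting and diarrhea percentages count everyone at risk at an interval's start as fully observed, so after month 24 a constant rate would read as declining

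*SAP*

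**What the plan says.** SAP 2.3.5.1, under the analysis of all TEAEs, plans the frequency of nausea, vomiting and diarrhea over time "using 3-month time intervals, i.e., [0-3] month, (3-6] month, (6-9] month, (9-12] month, etc". No last interval is named. In each interval "the numerator in the calculation of percentages will be the number of participants with at least 1 TEAE occurring in this time interval".

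There are two versions. Analysis (1) counts first events only, and its denominator is limited to those at risk at the interval's start "who did not experience a first event in the preceding intervals". Analysis (2) counts a participant again in later intervals, and there "the denominator for the calculation of percentages will be the number of participants at risk at the beginning of the time interval". A histogram by 3-month interval may accompany them. Neither version adjusts for people who leave during an interval. A Kaplan-Meier plot is planned for the same three terms, for first onset only.

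Three other parts of the SAP decide who leaves when:

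- Section 1.3 assumes "A recruitment period of approximately 12 months" and "estimated follow-up ranging from 24 to 36 months".
- The key definitions in 2.1 say of the close-out visit: "It is a fixed calendar time window".
- Section 2.1.4 and Appendix C (e) end the TEAE period, and AE censoring, 30 days after the last injection. Appendix C (e) uses the date of death if that is earlier.

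**The concern.** Participants enter over a year and stop together, so leaving part-way through an interval after month 24 is built into the design. Those who left before an interval began are correctly removed from its denominator. Those who leave during it stay in as whole persons, although their later events cannot be counted. The percentage then falls below the true 3-month risk, and falls further in each later interval as leavers make up more of those still at risk.

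The table exists to show how GI events change with time on drug. Protocol 2.3 describes nausea and vomiting in earlier studies as rising after the first injection and generally decreasing afterwards. A decline produced by the denominator would look like confirmation of that pattern at late times.

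**Working it through.** The documents give no figure for these percentages, so there is none to reproduce. The check asks what the rule would show if the true rate did not change.

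**Inputs**

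- Follow-up of 24 to 36 months (SAP 1.3). Uniform entry over 12 months is an assumption.
- TEAE window to last injection plus 30 days, taken as 1 month (SAP 2.1.4). The end of risk, T, is then uniform over months 25 to 37 for those still on IMP at close-out.
- Constant event hazard h: 2% per month and 0.2% per month, both assumed, to show a range.
- No early stopping in the main calculation; it is treated separately below.

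**Observed share of interval time**

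For an interval starting at month a, the share is the mean of min(T − a, 3)/3 among those with T > a.

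- (21-24] and earlier: nobody reaches close-out, so 100%.
- (24-27]: all at risk; 2/12 leave, between months 25 and 27, losing on average 1 of 3 months. 1 − (2/12)(1/3) = 94.4%.
- (27-30]: 10/12 at risk; 3/10 leave, losing half the interval on average. 1 − 0.30 × 0.5 = 85.0%.
- (30-33]: 7/12 at risk; 3/7 leave. 1 − (3/7)(0.5) = 78.6%.
- (33-36]: 4/12 at risk; 3/4 leave. 1 − 0.75 × 0.5 = 62.5%.
- (36-39]: 1/12 at risk; all leave within the first month. 0.5/3 = 16.7%.

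**What the SAP percentage would read**

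The true 3-month risk is 1 − exp(−3h): 5.82% at h = 0.02 and 0.598% at h = 0.002. The SAP figure is the mean of 1 − exp(−h × observed months) over those at risk at the start.

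| Interval | At risk at start | Share observed | Reads, true 5.82% | Reads, true 0.598% |
|---|---|---|---|---|
| (21-24] | 100% | 100% | 5.82% | 0.598% |
| (24-27] | 100% | 94% | 5.51% | 0.565% |
| (27-30] | 83% | 85% | 4.96% | 0.509% |
| (30-33] | 58% | 79% | 4.59% | 0.470% |
| (33-36] | 33% | 63% | 3.66% | 0.374% |
| (36-39] | 8% | 17% | 0.99% | 0.100% |

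Worked line for (33-36] at h = 0.02: one quarter have the full 5.82%. Three quarters leave evenly over the interval, and their average risk is 1 − (1 − exp(−0.06))/0.06 = 2.94%. So 0.25 × 5.82 + 0.75 × 2.94 = 3.66%.

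**Early stopping**

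With "2% annual early study discontinuation" alone, intervals before month 24 are about 99.7% observed. If IMP stopping were 10% per year in one arm and 20% in another (assumed), the shares in a pre-month-24 interval would be 98.7% and 97.3%. A true 5.82% would read 5.74% and 5.66%, a gap of about 0.1 percentage point.

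**Does the remedy work?**

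At h = 0.02, participants with at least one event per 100 observed patient-months come to 1.94 in (21-24], 1.94, 1.94, 1.95 and 1.95 in the next four intervals, and 1.99 in (36-39]: essentially flat. For analysis (1), with time counted to the first event, the rate is 2.00 throughout.

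The actuarial denominator, number at start minus half of those leaving (w/2), gives 6.01%, 5.83%, 5.84% and 5.86% against 5.82%. The slight excess in (24-27] arises because departures there start only at month 25. In (36-39] it fails (0.99/0.5 = 1.99%), because everyone leaves in the first month.

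**The case against.** The case for leaving the tables alone is fair in several respects.

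- *Descriptive only.* SAP 2.3.5 plans no hypothesis testing on safety data, and no claim uses these tables. This stands, and it limits the point to presentation.
- *Already handled for first events.* The Kaplan-Meier plot treats censoring properly for the same three terms, so the problem in analysis (1) matters less. It does not reach analysis (2) or the histogram, which have no censoring-adjusted counterpart.
- *GI events are expected early.* The eight intervals to month 24, including titration, are essentially untouched by the stagger. If late rates are low, the absolute error is small: at 0.2% per month it is at most about 0.2 percentage points to month 36. The relative decline remains.
- *The end date is event-driven.* The affected intervals may move. If close-out came 3 months earlier, the same shares would apply from month 21. The effect would shift, not vanish.

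A reader might also infer more than the documents support, in two ways. One is to end observation at close-out, which gives shares of 87.5%, 83%, 75% and 50%. That ignores the 30-day window in SAP 2.1.4, which is observed because participants still on IMP at close-out have a follow-up visit 6 weeks after the last dose. The other is that the comparison between arms is biased. Close-out is one calendar window for all arms under 1:1:1 randomization, so it is not. Differential IMP stopping could shift it, but by about 0.1 percentage point in the example above.

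**Conclusion.** The point holds as a minor one. The stated denominator makes a constant rate appear to fall after month 24, to about 63% of its true value by (33-36] and further in any residual interval. This affects analysis (2), the histogram and, less importantly, analysis (1). It distorts the descriptive time trend and has no bearing on efficacy conclusions or, through close-out, on the comparison between arms.

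The direction follows from the SAP's own rule and design. The sizes rest on uniform entry, the planned 24 to 36 months and a constant hazard. The absolute error depends on a late event rate that the documents do not give. The last intervals also rest on few participants: a third at risk at month 33 and a twelfth at month 36.

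**What to change.** In SAP 2.3.5.1, for each interval and arm, report participants with at least one event per 100 patient-months of TEAE-period time actually observed in that interval. For analysis (1), count time only to the first event. Keep n and the number at risk at the interval's start, and plot the histogram on the rate scale with the number at risk beneath.

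The number at start minus w/2 is an acceptable approximation if a percentage is preferred, but not for the final residual interval.

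The cost is a short wording change and a different denominator in the program. The dates needed are already defined in Appendix C, and the SAP already uses patient-year rates for MACE (2.3.4.1.2) and severe hypoglycemia (2.3.5.1). The one drawback is that a rate is slightly less simple to read than a percentage.
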